#### Informed Consent Procedures:

The control group data used for this objective is will be obtained through a DUA for existing data. We are requesting waiver of informed consent for the control group and a HIPAA waiver for this objective.

For the Caregiver telephone survey, a CIRB approved information consent sheet will be included in the recruitment packet left with the Veteran and Caregiver as detailed above. A waiver of written consent will be requested for the survey because the survey will be conducted over the phone and are considered minimal risk. Verbal informed consent will be obtained in conformation with the policies established by the CIRB Institutional Review Board in accordance with the Department of Health and Human Services Regulations regarding the protection of human subjects (45 CFR 46.116). The verbal consenting procedure is detailed in the survey document.

# Privacy and Confidentiality:

Please see the Data Assurances section of the protocol for a description of the security measures in place for all electronic data.

# **Objective 3**

In Objective 3 we will identify factors impacting VD-HCBS program implementation activities from multiple stakeholder vantage points (VA and ADNA) and throughout the implementation process by identifying specific strategies for effective program implementation within a range of contexts. Therefore, we will:

Objective 3a) elicit implementation strategies used based on a compilation published by the Expert Recommendations for Implementing Change project;

Objective 3b) examine how contextual factors impact implementation using the Consolidated Framework for Implementation Research;

Objective 3c) examine the relationship between implementation strategies, contextual factors and outcomes at individual and institutional levels.

As part of this objective, we will conduct individual interviews with VA and ADNA coordinators from 16 purposefully selected VA medical centers with recently established and existing VD-HCBS programs. The 32 coordinators will include 16 ADNA Coordinators and 16 VA coordinators from 16 VD-HCBS program sites. Whenever possible, each coordinator will be interviewed at two time points (64 total interviews). The first set of interviews with the coordinators, will be 2 to 4 months after GEC allows the program to begin enrolling Veterans (completion of the Lewin Group readiness review). The second set of interviews will be 6 months after the initial interview to obtain follow-up data about implementation process, compared to the initial startup time, implementation strategies that they have employed, and their evaluation of implementation success (See Interview Guides). If it is not possible to interview sites at 2months after GEC allowed to begin enrolling Veterans (completion of the Lewin Group readiness review), we will conduct one interview at least 6-months after readiness review. From the VA coordinators, we will request a local VAMC leader (n=16) and a VISN GEC leader (n=16) for one-time interviews (32 interviews). Additionally, we will ask the GEC VISN leads when we interview them to recommend local GEC contacts. Pair Interview Dropout. Our primary interest is in triangulating data from the VA and ADNA coordinators at a case level. However, there will be dropout and turnover in the coordinator positions. When there is dropout, we will seek to recruit another individual from the site to complete the pairwise analysis. If this is not possible, we will exclude that program site in the case-level analysis and continue to recruit until we have 16 program sites, with participation from both the VA and ADNA coordinators. We anticipate dropout of 25% in the pairwise analysis and are requesting permission to perform additional interviews at 4 sites (8 interviews)

Including the additional interviews to allow for the projected drop out rate, we estimate that a Total of 104 interviews will be conducted with a total of 72 individuals.

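### The four-site allowance for 25% pair dropout in Objective 3 yields 15 expected complete pairs, not 16, and does not fit the rule to recruit until there are 16

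*Combined protocol and SAP*

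**What the plan says.** All the figures are in Section 5.0, Objective 3, mostly under Pair Interview Dropout.

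- Target: "The 32 coordinators will include 16 ADNA Coordinators and 16 VA coordinators from 16 VD-HCBS program sites".
- Coordinator interviews: "Whenever possible, each coordinator will be interviewed at two time points (64 total interviews"). If the early window is missed at a site, "we will conduct one interview at least 6-months after readiness review".
- Leaders: "we will request a local VAMC leader (n=16) and a VISN GEC leader (n=16) for one-time interviews (32 interviews").
- Loss of a coordinator: the team first tries to recruit someone else from the same site. Only if that fails, "we will exclude that program site in the case-level analysis and continue to recruit until we have 16 program sites", with both coordinators taking part.
- Allowance: "We anticipate dropout of 25% in the pairwise analysis and are requesting permission to perform additional interviews at 4 sites (8 interviews").
- Totals: "we estimate that a Total of 104 interviews will be conducted with a total of 72 individuals".

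Section 7.0, Objective 3, makes the VA-ADNA pair the primary unit of analysis. It defines the institutional outcome for the QCA as the VD-HCBS share of Veterans in home and community-based care one year after program start. It also describes the QCA findings as generalizable and as a possible basis for helping sites that struggle.

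**The concern.** The allowance multiplies the target by the dropout rate. That gives the number of pairs expected to be lost from the first 16, but the sites brought in to replace them can lose a coordinator too. On the plan's own rate, the request falls short of the 16 complete pairs it is meant to secure. The open-ended recruitment rule does not close the gap, because permission is sought for only four more sites.

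A second, narrower matter is which sites leave the analysis. A site is excluded when a lost coordinator cannot be replaced from within. Section 2.0 lists designated VAMC staff among the mechanisms that earlier interviews linked to successful partnerships, so a site unable to fill the role may differ in the very thing under study. No comparison of excluded with retained sites is described in Section 5.0 or 7.0. If the excluded sites implement less well, the QCA describes the better-staffed sites, while the plan proposes to apply it to struggling ones.

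**Working it through.** **Inputs** (Section 5.0, Objective 3): 16 target pairs; 25% dropout, read as a pair-level rate because it is stated for the pairwise analysis; 64 coordinator interviews with 32 coordinators; 32 leader interviews with 32 leaders; 4 extra sites with 8 interviews.

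**Reproducing the plan's figures**
- Extra sites: 16 × 0.25 = 4, so 20 sites.
- Interviews: 64 + 32 + 8 = 104.
- Individuals: 32 + 32 + 8 = 72.

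All match.

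**Expected complete pairs from 20 sites**
- If added sites never drop out: 16 × 0.75 + 4 = 12 + 4 = 16. This is what the allowance assumes.
- If added sites drop out at the same rate: 12 + 4 × 0.75 = 15, that is, 20 × 0.75.
- If exactly 4 of the first 16 pairs are lost, reaching 16 requires all four replacement pairs to complete: 0.75⁴ = 0.32.

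**Sites needed**
- Number to recruit for 16 expected pairs: 16/(1 − 0.25) = 21.3, so 22 sites, or 6 extra. The expected yield is then 22 × 0.75 = 16.5.
- If recruitment continues until 16 pairs are complete, the mean number of sites used is also 16/0.75 = 21.3.

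**Chance of at least 16 complete pairs**, binomial with completion probability 0.75 and independent sites:

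| Sites | Expected pairs | P(at least 16) |
|---|---|---|
| 20 | 15.0 | 0.41 |
| 22 | 16.5 | 0.70 |
| 24 | 18.0 | 0.88 |

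**Totals with six extra sites**, keeping the plan's 2 additional interviews (8/4) and 2 additional individuals (8/4) per extra site:
- Interviews: 64 + 32 + 12 = 108.
- Individuals: 32 + 32 + 12 = 76.

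**Sites excluded**, if the 25% is the loss left after in-site replacement has been tried: 20 × 0.25 = 5 of 20, or 22 × 0.25 = 5.5 of 22.

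**The case against.** The best defence is that the recruitment rule is sequential and aims at 16, that the totals are given as estimates, and that 16 is a purposive number of cases rather than a powered sample size. All of that is true. It limits the importance of the point but does not reconcile an open-ended rule with a request for four sites. The binomial figures also assume independent losses and one rate at all sites, neither of which the plan states.

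Three stronger readings are tempting, and the documents do not support them.

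- *Replacement coordinators are counted at one interview each, so the total should be 112 (or 120 with six extra sites).* Eight interviews with eight added people does suggest this. But both totals also follow from two rounds at replacement sites if the four lost sites stop after round one. Interviews: 12 × 2 × 2 + 4 × 2 × 1 + 4 × 2 × 2 + 32 = 48 + 8 + 16 + 32 = 104. Individuals: 24 + 8 + 8 + 32 = 72. The plan does not say how the 8 was built, two interviews are planned only where feasible, and a one-interview fallback exists.
- *Sites with turnover are removed.* They are not removed as such. In-site replacement comes first, and a site that finds a successor stays. The exclusion also applies only to the case-level analysis.
- *The 25% is a rate per coordinator.* If so, and if losses were independent, pair completion would be 0.75² = 0.5625 and 20 sites would give 11.25 pairs. The text attaches the rate to the pairwise analysis, so this reading is not supported.

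**Conclusion.** The point holds and is minor. At the plan's own pair-level rate, applied to added sites as well as the first 16, the allowance is one expected complete pair short (15 against 16), or two sites after rounding up (20 against 22). Reaching 16 from 20 sites is somewhat less likely than not (about 41%) under independence. If added sites were immune to dropout the allowance would suffice, but the plan gives no reason to expect that. Nothing here shows that 15 rather than 16 cases would change a QCA conclusion.

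The stated 104 interviews and 72 individuals are consistent with a four-site allowance and are not in error.

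That exclusion of sites unable to replace a coordinator is informative is a plausible risk, not a demonstrated bias. It deserves a check because the plan claims generalizability.

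**What to change.** 1. Reconcile the allowance with the recruitment rule in one of two ways:
   - keep four extra sites, state the expected yield from 20 sites as 15 complete pairs, and say that recruitment stops at 20; or
   - restate the allowance as six extra sites (22 in total, 16.5 expected pairs), with totals of 108 interviews and 76 individuals. It should be said that 22 sites meet the target in expectation, with about a 70% chance of at least 16 pairs.
2. Compare one-year uptake, as already defined for the QCA, between included sites and sites excluded because a lost coordinator could not be replaced. With roughly five excluded sites this can only be descriptive. Report it as a limit on the generalizability of the QCA.
3. Optional: a second QCA run that keeps sites with one remaining coordinator as single-informant cases. This departs from the declared unit, the VA-ADNA pair, so it should be labelled as a sensitivity analysis.

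The cost is a few restated figures in the submission and one descriptive table. The second option in item 1 also means fieldwork at up to two more sites. The uptake comparison needs no new interviews.

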## **Recruitment Methods:**

We will purposefully select 16 VAMCs based on criteria related to quality of VA-ADNA collaboration and standard practice, identified as factors impacting implementation in our prior evaluations. For each case, we will conduct individual interviews with VA VD-HCBS coordinators and associated ADNA coordinators plus additional key decision makers identified by coordinators and GEC points-of-contact for the VISNs that cover the VD-HCBS programs in our sample. Coordinators will be those reported by The Lewin Group, the contractor responsible for Technical Assistance, as the contact person for the VD-HCBS program. Additional respondents will be identified when coordinators are asked to name their local VAMC leader and a VISN GEC leader as described above. Once potential participants have been identified within eligible VAMCs and ADNAs, they will be sent an introductory letter to their work email address. The letter will inform them about the interview, the goal of the interview, that the interview will be recorded for transcription purposes only, that they may contact a Providence-based project staff member to address any questions or concerns they may have prior to participating or to schedule an interview, and that unless a refusal is received they will be contacted at their work telephone number a week after the email is sent to schedule an interview. Participants will also be informed that they may be required to do this interview on offduty time unless their supervisor approves on-duty time. If they are willing to participate, a phone call will be scheduled.

## Informed Consent Procedures:

When Coordinators or key informants respond to the invitation letter or subsequent recruitment phone call and state that they want to participate, a member of the project team will send them a CIRB approved information consent sheet about the interview. This information consent sheet will include information about their rights as study participants. At the time of the interview, the interviewer will confirm that the participant received the written information about the study and consent process. Then the interviewer will reiterate key parts of the informed consent information that were sent via email when the interview was scheduled, including the purpose of the study, the key informant's rights as a study participant, and the confidentiality of the interview. The interviewer will invite the participant to ask questions about the consent information. The interviewer will then request verbal consent to proceed with the interview and ask permission to audio-record the interview for transcription purposes. If the participant verbally consents, the interview can be conducted. Interviewers will keep a verbal consent log.

We are requesting a waiver of documentation of consent for these telephone interviews.

#### Privacy and Confidentiality:

To help mitigate the risks to interviewees in Objective 3 telephone interviews will be conducted in private settings as one-on-one interviews with the interviewer. A research associate may be present as well to take notes, and this individual will be identified and introduced to the respondent. The information gained during the interviews will not be used to evaluate quality of care. Neither the employee's supervisors nor peers nor the clients will have access to the data. Data will remain confidential. Identifiers, including first and last name and the name of their associated VAMC, will not be elicited from interview respondents during interview recordings. After transcription, the transcripts will be read by a project team member to ensure that any identifiable or sensitive data that participants volunteer during the interviews is removed prior to analysis. Interview responses will be aggregated so individual sites and interviewees cannot be identified. No individually identifiable information will be published or disclosed, unless required by law.

To protect participants against risk after interview data have been collected, we will take a variety of measures to ensure confidentiality. In all records, participants will be assigned unique identifiers. The crosswalk linking unique identifiers to participants, the verbal consent log, as well as all interview recordings and transcripts will be stored electronically in a password protected, restricted-use folder on a Providence VA server in a restricted access service directory, in a restricted folder with access limited to project staff. Any hard copies of any of these files will be stored at the VA in a locked file cabinet in the locked office of study personnel. When the data are reported, neither VAMCs nor interviewees will be identified in any way, to preserve anonymity of respondents.

Please see the Data Assurances section of the protocol for a description of the security measures in place for all electronic data.

6.0 VD-HCBS Contextual Information. GEC, ACL, and The Lewin Group regularly host training and check-in activities via conference call or webinar. GEC, ACL and The Lewin Group have given approval for an evaluator to join the conference calls and webinars for the purpose of collecting information about the specific implementation issues that are discussed as VD-HCBS programs are developing and operating. The evaluator will take notes on the overall tone, topics, and attitude of these calls. Notes will not include quotations, names, or information on individual sites. Information gained from these calls will be for the sole purpose of identifying patterns of implementation experiences.

## 7.0 Data Analysis

#### **Objective 1:**

Quantitative Analysis of Veteran Survey Data - We will analyze the quantitative data from the Veteran Assessment survey data by calculating descriptive statistics and means for the survey items. We will compare the responses at baseline to responses at 3 months, and to responses at 12 months to gauge early and long-term change in the various domains. We will also calculate differences in change by Veteran characteristics, including care arrangement, functional impairment, socioeconomics, and demographics. This descriptive pre-post analysis will provide a first look at the impact of the VD-HCBS program on Veterans. Lastly, we will use finite mixture models to identify subgroups of Veterans that have similar trends in outcomes. Finite mixture models are clustering methods based upon a statistical model with stochastic elements. Formally, they can be written as  $p(Y_i) =$  $\sum_{i=1}^{J} \pi_i F(Y|G_i = j)$ , where Yi is a vector of outcomes for Veteran i,  $\pi_j$  is the proportion of subgroups j among Veterans, Gi is an unknown group classification for Veteran i, F is the distribution of the outcome at the that subpopulation, and J are the number of subpopulations. We will examine different possible values for the number of subgroups, and select the number with the highest Bayesian Information Criterion (BIC). Our initial model for F will be multivariate Gaussian distribution, which may require appropriate transformations of some of the outcomes (e.g., log). If the Gaussian model will not provide a good fit for the data, we will examine other possible models such as a mixture of t distributions, or a mixture of skewed-Normal distributions. After the model identifies the possible subgroups, we will attempt to describe them by examining the trends in the observed outcomes (e.g., Veterans with increasing outcome trends overall, patients with moderately increasing outcomes at 3 weeks but stable at 12 months). These subgroups will enable us to identify the possible patterns that exist among Veterans exposed to the VD-HCBS program. Following this identification, we will examine qualitative (see below) or quantitative variables that are possibly associated with these patterns, so that we could provide further understanding on the possible effectiveness of the program.

*Qualitative Analysis* - The team will read interview transcripts multiple times and independently make initial codes, then resolve coding differences through a process of deliberation and consensus. In subsequent and repeated bi-weekly meetings we will refine code definitions and reach consensus about the interpretation of the material, with our decisions recorded in an audit trail. Continuing this process, codes will be clustered into related categories using conventional content analysis to generate themes that represent successive levels of interpretation. Subsequent analysis will connect common codes and themes across Veterans and VAMCs. In the search for alternative interpretations and to

provide analytic rigor about the validity of findings, findings will be challenged by team members to ensure comparability of perspectives. [name] will oversee the analysis and the team will report on the process during bi-weekly meetings.

*Connect Qualitative and Quantitative Data* - We will use evidence from both the quantitative and qualitative analysis to portray the impact of the VD-HCBS program on Veterans. We will analyze the quantitative and qualitative data separately and then integrate the results to present a comprehensive picture of how the program has impacted Veterans, both in terms of satisfaction and their life experience. Specifically, we will use our qualitative findings to provide depth of understanding and quantitative data to provide breadth of understanding Veterans' experiences with the VD-HCBS program. With this parallel mixed method design, we will be able to provide explanation and description of Veterans' experiences and the ways by which the VD-HCBS program impacts their lives.

Please see the Data Assurances section of the protocol for a description of the security measures in place for all data.

